4.2.10 Clinical Benefit after 16 Cycles

The number and percentage of participants with continuing clinical benefit after 16 cycles of atezolizumab will be summarized as per [Table 2](#) in Section 1.1 of the SAP. Patients who did not yet reach Cycle 16 but are still ongoing at the time of the analysis will be excluded. Similarly, patients who did not receive any treatment will be excluded from the analysis. Patients who discontinued or died before Cycle 16 will be considered as having no ongoing clinical benefit.

This analysis will be based on the FAS. In addition, as a part of exploratory analysis, the analysis may also be stratified by disease stage at study entry.

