3.2 END OF STUDY AND LENGTH OF STUDY

The end of the study is defined the Last Participant, Last Visit (LPLV), which is estimated to occur one year after the last participant is randomized or the date at which the last data point required for the final statistical analysis or safety follow-up is received from the last participant, whichever occurs later.

In addition, the Sponsor may decide to terminate the study at any time.

The study is estimated to last approximately 2 years.

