4.6.3 Study Discontinuation

The Sponsor has the right to terminate this study at any time. Reasons for terminating the study may include, but are not limited to, the following:

- The incidence or severity of adverse events in this or other studies indicates a potential health hazard to participants
- Participant enrollment is unsatisfactory
- Development of atezolizumab SC formulation is discontinued

The Sponsor will notify the investigator if the Sponsor decides to discontinue the study.

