4.1 GENERAL CONSIDERATIONS

The primary analysis will take place when all study participants have completed their last study treatment administration in the Treatment Cross-over Period. Summaries of secondary study endpoints, including PK and ADA measurements, participant-reported TASQ and EORTC QLQ-C30 responses, selection of treatment administration method for the Treatment Continuation Period, HCP reported HCPQ responses, and safety endpoints will be included in the primary analysis, based on all data up to the clinical cut-off date.

The final study analysis that includes all secondary endpoints including all questionnaires, PK, ADA, and safety endpoints will be conducted after the end of the study (i.e., when all patients have received 16 cycles of atezolizumab or discontinued study treatment).

Summaries of participants' preference, analysis of PROs, including the primary endpoint, HCP reported outcomes and clinical benefit, as well as sensitivity analysis for preference and satisfaction, will be based on the FAS, according to the treatment sequence assigned.

All safety analyses will be performed in the safety-evaluable population, unless otherwise specified. Participants will be analyzed according to the treatment they actually received. In case of protocol deviations leading to a treatment sequence with more than one treatment switch, participants will be analyzed according to the treatment sequence assigned.

Continuous variables will be summarized by the mean, standard deviation, median and range (minimum and maximum). Categorical variables will be summarized by number/percentage of participants.

Unless otherwise stated, baseline values are the last available data obtained prior to the patient receiving the first dose of study treatment (or at screening, for patients who were not treated).

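### Does the Cycle-16 clinical-benefit rule bias the percentage downward by dropping participants who are still on treatment?

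*SAP*

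**What the plan says.** The endpoint is the percentage of participants whose clinical benefit is continuing after 16 cycles, as judged by the investigator (Protocol 2.2; SAP Table 2). SAP 4.2.10 sets three rules on the Full Analysis Set:

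- Ongoing before Cycle 16: "Patients who did not yet reach Cycle 16 but are still ongoing at the time of the analysis will be excluded".
- Stopped or died before Cycle 16: "Patients who discontinued or died before Cycle 16 will be considered as having no ongoing clinical benefit".
- Never treated: left out.

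On timing, SAP 4.1 describes two analyses and SAP 4.5 plans no interim.

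- The primary analysis follows the last Cycle 6 dose. It names certain secondary summaries that "will be included in the primary analysis, based on all data up to the clinical cut-off date". Clinical benefit is not among those named.
- "The final study analysis that includes all secondary endpoints" comes after the end of the study, which the same sentence explains as the point "when all patients have received 16 cycles of atezolizumab or discontinued study treatment".

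Protocol Section 6 limits the secondary summaries in the primary analysis to Cycle 7 Day 1. Protocol 3.2 ends the study at the later of two dates: the last visit, put at about a year after the last randomisation, and receipt of the last data point that the final analysis or safety follow-up needs. It adds that "the Sponsor may decide to terminate the study at any time". Protocol 4.6.3 gives reasons for stopping the study, among them "Participant enrollment is unsatisfactory".

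**The concern.** The first two rules treat people with short follow-up unequally. A recent entrant who is doing well is removed; a recent entrant who has stopped is kept as a failure. Whether someone enters the denominator then depends on the outcome, which is a familiar source of bias. The reported percentage would reflect accrual speed and cut-off date as well as benefit.

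Early termination adds an ambiguity. Protocol 4.6.2 lists termination of the study or closure of a site among the reasons for leaving the study. A participant stopped for that reason alone could be read as ongoing (excluded) or as discontinued (a failure).

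What would be at stake is one secondary percentage, with no test attached.

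**Working it through.** The documents give no expected value for this endpoint, so there is no planned figure to reproduce. The sample size (126 evaluable, 175 randomised) rests on preference alone.

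**Direction.** Let S be those who reach Cycle 16 with benefit. Split the failures into F_m (entered early enough to have reached Cycle 16) and F_i (entered too late). The rule reports S / (S + F_m + F_i), which cannot exceed S / (S + F_m). With S above zero, the two are equal only when F_i = 0. This needs no assumption about accrual or hazard.

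**When the rule acts.** Cycles last 21 days, so Cycle 16 Day 1 falls 15 × 21 = 315 days after the first dose if there are no delays.

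- Final analysis: by definition everyone has had 16 cycles or has stopped. The exclusion set is empty and the bias is 0. An end of study about one year after the last randomisation leaves room even for the end of Cycle 16 (16 × 21 = 336 days), and the later-of-two-dates wording covers delays.
- Primary analysis: at the earliest, 5 × 21 = 105 days after the last participant's first dose. The rule would exclude people here if the percentage were produced.

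**Size if it were produced early (illustration only).** Assumptions not in the documents: uniform entry, a constant discontinuation hazard, no dose delays. Accrual of about 364 days is inferred from Protocol 3.2: "The study is estimated to last approximately 2 years", less about one year after the last randomisation. Take N = 175, a true value p = 0.60 and a cut-off at day 105, so potential follow-up F is uniform on 105 to 469 days.

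- P(F ≥ 315) = (469 − 315)/364 = 0.423.
- Successes: 0.423 × 0.60 × 175 = 44.4.
- Failures with enough follow-up: 0.423 × 0.40 × 175 = 29.6.
- Failures without it: hazard = −ln(0.6)/315 = 0.00162 per day. The integral of the survival curve from 105 to 315 is (0.6^(1/3) − 0.6)/0.00162 = 150.1, so (210 − 150.1)/364 × 175 = 28.8.
- Excluded: 175 − 44.4 − 29.6 − 28.8 = 72.2.
- Reported: 44.4/(44.4 + 29.6 + 28.8) = 43.2%, a bias of −16.8 points.

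Reported percentage by cut-off, with 52-week accrual (37% is 0.72³, extrapolating the SAP's 28% non-evaluable allowance over three 105-day spans):

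| Weeks after last entry | True 37% | True 60% | True 80% |
|---|---|---|---|
| 15 | 22.7 | 43.2 | 67.4 |
| 26 | 28.5 | 50.4 | 73.2 |
| 40 | 35.1 | 57.7 | 78.4 |
| 45 | unbiased | 60.0 | 80.0 |

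The size has no useful ceiling. At 15 weeks and a true 60%, accrual of 65, 52 and 39 weeks gives biases of 11.8, 16.8 and 29.2 points. With 240-day accrual the worst case is about 42 points. With 210 days or less nobody has passed day 315 (210 + 105 = 315), and the rule shows 0% whatever the truth.

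**Early termination.** If the study stopped at day 364 with accrual still open, P(F ≥ 315) = 49/364 = 0.135, and a true 60% would show as 25.1%. Counting closure-related stops as failures instead gives 0.135 × 0.60 = 8.1%.

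**The case for a change.** The best case for a change runs as follows. The SAP's list for the primary analysis is open-ended and uses all data to the cut-off. The SAP also says that it supersedes the protocol's analyses, so the Cycle 7 Day 1 limit may not bind. The exclusion sentence does nothing at the final analysis, which suggests that its author had an earlier look in mind. Termination is allowed at any time, and a denominator chosen after the data are seen is what a SAP should prevent. The remedy costs a few sentences and no data.

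What stands is the direction of the bias and the ambiguity about stops caused only by closure. What does not stand is the step to a needed amendment. No text schedules this percentage before the final analysis. The named list omits it, and the protocol's limit argues against it. Early termination would cut short most fixed-time endpoints, not this one in particular, and a closing analysis would need its own account of who was assessable.

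A replacement rule is not free of choices either. A 315-day entry limit marks the start of Cycle 16, whereas benefit after 16 cycles may mean day 336. In the illustration above, the early denominator falls to about 74 of 175 at 315 days, 64 at 336, and 34 at 399 (315 plus the 12-week hold in Protocol Appendix 9).

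**Conclusion.** The mechanism is real but idle in the plan as written. At the scheduled final analysis the bias is exactly zero, and a revised rule would give the same percentage. The figures of 12 to 29 points for a true 60% describe a summary that nobody has planned, under accrual and hazard assumptions that the documents do not supply.

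This conclusion rests on two conditions: the final analysis is run at the point SAP 4.1 defines, and the endpoint is not brought forward. If either failed, an analyst would sensibly restrict numerator and denominator to participants first dosed long enough ago to have completed 16 cycles, and would state how closure-related stops were classed. Writing that down now is optional. Counting every stop before Cycle 16 as no benefit does still act at the final analysis, but that is a stated definition of the endpoint and a separate matter from the exclusion.

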4.3 SAFETY ANALYSES

Unless specified otherwise, safety analyses described below will be conducted for the safety-evaluable population.

For safety analyses, 2 treatment periods will be defined. Within the cross-over treatment period, 2 subperiods may also be used for the analysis, when appropriate.

- **Cross-over period:** maximum of 6 cycles of Atezolizumab, SC (maximum 3 cycles) and IV (maximum 3 cycles). The cross-over period consists of 2 subperiods:
 - Cycle 1 to Cycle 3
 - Cycle 4 to Cycle 6
- **Continuation period:** for patients who completed the cross-over period, the continuation period will consist of additional cycles of Atezolizumab IV or SC, up to a total of 16 cycles for early NSCLC or until loss of clinical benefit for Stage IV NSCLC.

4.3.1 Extent of Exposure

Study treatment exposure (such as treatment duration, total dose received, and number of cycles and dose modifications) will be summarized by treatment period and by treatment sequence (IV/SC, SC/IV) in the cross-over, as well as by treatment route (IV, SC) in the continuation period.

The total number of cycles initiated will be summarized both by descriptive statistics and by presenting the number and percentage of patients in each category. The number and percentage of patients who have received their 6th cycle will also be summarized. A patient will be considered as having initiated a cycle if at least one (non-null) dose of study drug has been administered in the corresponding cycle.

Study drug administration details will be summarized by descriptive statistics and will include percentage of patients with cycles delayed, average number of days delayed, percentage of patients with dose modification and percentage of patients with injection or infusion modification.

4.3.2 Adverse Events

After informed consent has been obtained but prior to initiation of study treatment, only serious adverse events caused by a protocol-mandated intervention (e.g., invasive procedures such as biopsies, discontinuation of medications) should be reported.

After initiation of study treatment, all adverse events will be reported until 30 days after the final dose of study treatment or until initiation of new systemic anti-cancer therapy, whichever occurs first, and serious adverse events and adverse events of special interest will continue to be reported until 90 days after the final dose of study treatment or until initiation of new systemic anti-cancer therapy, whichever occurs first.

After the end of the reporting period for serious adverse events and adverse events of special interest (defined as 90 days after the final dose of study treatment or until initiation of new systemic anti-cancer therapy, whichever occurs first), all deaths, regardless of cause, should be reported through use of the Long-Term Survival Follow-Up eCRF.

All verbatim adverse event terms will be mapped to Medical Dictionary for Regulatory Activities thesaurus terms, and adverse event severity will be graded according to NCI CTCAE v5.0. All adverse events, serious adverse events, adverse events leading to death, adverse events of special interest, and adverse events leading to study treatment discontinuation that occur on or after the first dose of study treatment (i.e., treatment-emergent adverse events) will be summarized by mapped term, appropriate thesaurus level, and severity grade. For events of varying severity, the highest grade will be used in the summaries. Deaths and cause of death will be summarized.

To evaluate the safety of switching from atezolizumab SC to atezolizumab IV and from atezolizumab IV to atezolizumab SC, adverse event summaries will also be produced for the Treatment Cross-over Period by treatment arm and treatment period, as well as potentially by cycle. In addition, summaries of AE rate adjusted for patient-years at risk may be produced by treatment arm and treatment period.

An adverse event will be allocated to the treatment received on or before the adverse event start date.

Adverse events that started during the first three cycles of the Treatment Cross-over Period and continued into subsequent cycles (even if the adverse event changed severity grade) will be summarized under the route of administration during which it first occurred. These adverse events will be flagged in listings.

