Atezolizumab will be administered on Day 1 of each 21-day cycle. Participants will receive atezolizumab according to their assigned route of administration (i.e., SC or IV) for the first three treatment cycles. At Cycle 4, participants will cross-over and receive atezolizumab administered according to the alternative route of administration for Cycles 4–6. This period of 3+3 cycles in both treatment arms constitutes the study Treatment Cross-over Period.

After Cycle 6, participants will select how they would like atezolizumab to be administered (SC or IV) for the Treatment Continuation Period. The Treatment Continuation Period will continue until Cycle 16 for participants with early-stage NSCLC or until loss of clinical benefit, as determined by the investigator according to local standard of care, for patients with advanced NSCLC.

Participants will undergo an End of Treatment Visit within 30 days after completing study treatment and will enter *the safety follow-up period*. *Safety follow-up should occur approximately 90 days after the last dose of study treatment. Thereafter, participants will be contacted for survival status and to collect details of new anti-cancer therapy, if any.*

Participant preference will be assessed based on the PPQ (administered following treatment administration on Day 1, Cycle 6 of the Treatment Cross-over Period). Treatment satisfaction will be assessed based on the TASQ (administered following treatment administration on Day 1 of Cycles 3 and 6 of the Treatment Cross-over Period). Healthcare professionals will record their perception of time/resource use and convenience of treatment administration completing the HCPQs. Perception of time/resource use will be captured during the Treatment Cross-over Period and perception of convenience will be captured after administration of each participant's treatment Cycle 6. Health-related quality of life will be assessed using the EORTC QLQ-C30 completed during the Treatment Cross-over Period (at Cycle 1, Cycle 3, and Cycle 6), during the Treatment Continuation Period (at Cycle 7, Cycle 10, Cycle 13, and Cycle 16), and at the end of study treatment visit. Health utilities will be collected using the EQ-5D-5L questionnaire at the same time points as the EORTC QLQ-C30. The study questionnaires are provided in [Appendix 4](#), [Appendix 5](#), and [Appendix 6](#).

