5.3.5.2 Diagnosis versus Signs and Symptoms

A diagnosis (if known) should be recorded on the Adverse Event eCRF rather than individual signs and symptoms (e.g., record only liver failure or hepatitis rather than jaundice, asterixis, and elevated transaminases). However, if a constellation of signs and/or symptoms cannot be medically characterized as a single diagnosis or syndrome at the time of reporting, each individual event should be recorded on the Adverse Event eCRF. If a diagnosis is subsequently established, all previously reported adverse events based on signs and symptoms should be nullified and replaced by one adverse event report based on the single diagnosis, with a starting date that corresponds to the starting date of the first symptom of the eventual diagnosis.

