Appendix 1: Schedule of Activities

Treatment cycle	Screening ^a	Treatment Cross-over Period						Treatment Continuation Period	End of treatment visit ^c	Follow-up telephone call ^d
		1	2	3	4	5	6	Cycle 7 onwards ^b		
Day	-28 to -1	1 (±3 days)						1 (±3 days)	≤ 30 days from last study dose	90 days from last study dose
Concomitant medications ^{aa}	x	Collect on an ongoing basis								
Adverse events ^{bb}	x	Collect on an ongoing basis								
Study treatment administration										
Atezolizumab SC ^{cc}		Arm A only			Arm B only			According to participant choice ^{dd}		
Atezolizumab IV ^{cc}		Arm B only			Arm A only					
Tumor assessment	x ^{ee}	x ^{ff}								
PK samples		See Appendix 2 for detailed schedule								
ADA samples		See Appendix 2 for detailed schedule								

ADA=anti-drug antibody; aPTT=activated partial thromboplastin time; eCRF=electronic Case Report Form; EORTC QLQ-C30=European Organisation for Research and Treatment of Cancer Quality of Life Questionnaire; HBcAb=hepatitis B core antibody; HBsAb=hepatitis B surface antibody; HBsAg=hepatitis B surface antigen; HBV=hepatitis B virus; HCPQ=Healthcare Professional Questionnaire; HCV=hepatitis C virus; INR=International Normalized Ratio; NA=not applicable; PK=pharmacokinetic; PPQ=Patient Preference Questionnaire; TASQ-IV/SC=Therapy Administration Satisfaction Questionnaire for Intravenous Administration / Subcutaneous Administration; TSH=thyroid-stimulating hormone.

Notes: On treatment days, all assessments should be performed prior to dosing, unless otherwise specified.

^a Results of standard-of-care assessments performed prior to obtaining informed consent may be used (see specific assessments for allowed interval); such assessments do not need to be repeated for screening. Participants who do not meet the criteria for participation in this study may qualify for two re-screening opportunities (for a total of three screenings per participant) at the investigator's discretion, as described in Section 3.1.1.

^b For up to a total of 16 cycles for patients with early-stage NSCLC or until loss of clinical benefit, as determined by the investigator according to local standard of care, for patients with advanced NSCLC.

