Appendix 1: Schedule of Activities

- q All women of childbearing potential will have a serum pregnancy test at screening, within 14 days prior to initiation of study treatment. Urine pregnancy tests (or serum, if urine is not feasible) will be performed at specified subsequent visits during treatment, at the treatment discontinuation visit, and may be required beyond treatment discontinuation, monthly for 5 months after the final dose of atezolizumab. Pregnancy tests after study treatment discontinuation can be performed at home. If a urine pregnancy test is positive, it must be confirmed by a serum pregnancy test.
- r In accordance with country-specific health authority mandates, pregnancy tests may be required beyond treatment discontinuation, monthly for 5 months after the final dose of atezolizumab. Pregnancy tests after study treatment discontinuation can be performed at home. If a home urine pregnancy test is positive, it must be confirmed by a serum pregnancy test and if confirmed, immediately communicated to the treating physician.
- s TSH, free T3 (or total T3 for sites where free T3 is not performed), and free T4 will be assessed on Day 1 of Cycle 1 and every four cycles thereafter (i.e., Cycles 5, 9, 13, etc.).
- t At screening, participants will be tested for HIV, HBsAg, HBsAb, total HBcAb, and HCV antibody. If a participant has negative HBsAg and HBsAb tests and a positive total HBcAb test at screening, an HBV DNA test must also be performed. If a participant has a positive HCV antibody test at screening, an HCV RNA test must also be performed.
- u Urinalysis includes pH, specific gravity, glucose, protein, ketones, and blood; dipstick permitted.
- v Urinalysis should be performed as clinically indicated during study treatment.
- w The Patient Preference Questionnaire (PPQ) must be completed following study treatment administration on Day 1 of Cycle 6 of the Treatment Cross-over Period. Participants who discontinued study treatment prior to study treatment Cycle 6 should complete the questionnaire at the time of discontinuation as long as they have received at least one dose of atezolizumab SC and atezolizumab IV post-randomization.

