4.3.3 Additional Safety Assessments

4.3.3.1 Laboratory Data

Laboratory data will be summarized by treatment period, by treatment sequence and overall. Selected laboratory data will be graded according to NCI CTCAE v5.0 and will be summarized descriptively. Shift tables from baseline to worst post-baseline values will also be presented.

Potential Hy's law patients will be listed based on the laboratory data only: treatment-emergent elevated ALT or AST ($>3 \times$ baseline value) in combination with elevated total bilirubin ($>2 \times$ upper limit of normal [ULN]).

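### The rule for allocating adverse events to a route does not settle findings from the pre-dose assessments at the Cycle 4 switch visit, and its natural reading counts them under the wrong route

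*SAP*

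**What the plan says.** SAP 4.3.2 sets the rule: "An adverse event will be allocated to the treatment received on or before the adverse event start date". Protocol 6.5.1 uses the same words. Neither place mentions clock time, a pre- or post-dose marker, or a choice between two doses that both meet the condition. A companion rule in SAP 4.3.2 says that an event which began in the first three cycles and carried on "will be summarized under the route of administration during which it first occurred".

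The timing comes from the protocol. Section 3.1.1: "Atezolizumab will be administered on Day 1 of each 21-day cycle", and "At Cycle 4, participants will cross-over and receive atezolizumab administered according to the alternative route of administration for Cycles 4–6". The notes to Appendix 1: "On treatment days, all assessments should be performed prior to dosing, unless otherwise specified". Haematology, chemistry, vital signs and a limited examination are scheduled on Day 1 of every cycle. For thyroid function, footnote s says the tests "will be assessed on Day 1 of Cycle 1 and every four cycles thereafter (i.e., Cycles 5, 9, 13, etc"; the schedule also shows them at screening and at the end of treatment visit.

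The rule feeds the second safety objective, the safety of switching. SAP 4.3.2 plans adverse event summaries of the cross-over by arm and treatment period, and possibly by cycle. Inside the cross-over, a split by period can only mean Cycles 1–3 against Cycles 4–6. For laboratory data, SAP 4.3.3.1 says: "Laboratory data will be summarized by treatment period, by treatment sequence and overall".

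**The concern.** Cycle 4 Day 1 is both the last look at the first route and the date of the first dose by the second. A new abnormality in that morning's blood sample cannot have been caused by a dose not yet given. The allocation rule uses only the calendar date, and on that date the new route has been received. A programmer who implements the rule as the latest dose date not after the onset date will place the event after the switch.

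This happens in both arms: the finding moves to IV in Arm A and to SC in Arm B. Each arm would then show more visit-detected events after the change of route than before it. That is the pattern a reader of the switching tables looks for as a sign of harm. If a programmer settles the tie differently, the tables change with no change in the data.

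**Working it through.** The plan gives no figure on this point, so there is none to reproduce. The check sets the rule against the visit schedule.

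**Inputs.** 21-day cycles with the dose on Day 1, and the switch at Cycle 4 (Protocol 3.1.1). Treatment-day assessments before dosing (Protocol Appendix 1). Allocation by start date (SAP 4.3.2).

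**Step 1: allocate each scheduled pre-dose Day 1 visit in two ways.**

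| Visit | By last dose given before the assessment | By latest dose on or before the date |
|---|---|---|
| Cycle 2 | first route | first route |
| Cycle 3 | first route | first route |
| Cycle 4 | first route | second route |
| Cycle 5 | second route | second route |
| Cycle 6 | second route | second route |
| Cycle 7 | second route | continuation |

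By date the split is 2 visits v 3. By the last dose before the assessment it is 3 v 3, for participants who reach Cycle 7.

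**Step 2: exposure behind a Cycle 4 Day 1 finding.** Three cycles × 21 days = 63 days since the first dose, all 63 on the first route (63/63 = 100%).

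**Step 3: size.** Assume a detection probability q at each visit, equal at all visits, with no route effect and no dropout. Expected findings per 100 participants are 100 × 2q before the switch and 100 × 3q after it, a ratio of 3/2 = 1.5.

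| q (assumed) | Before | After | Each half, by last dose before the assessment |
|---|---|---|---|
| 2% | 4 | 6 | 6 |
| 5% | 10 | 15 | 15 |
| 10% | 20 | 30 | 30 |

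If participants with at least one finding are counted, and visits are independent, the ratio is a little lower. At q = 10%: (1 − 0.9³)/(1 − 0.9²) = 0.271/0.19 = 1.43. Hence up to 50%.

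**Step 4: pooled SC v IV.** Take equal arms, with s and i the detection rates per visit after an SC and an IV dose. Visits labelled SC are Arm A Cycles 2 and 3 (2s) plus Arm B Cycles 4, 5 and 6 (i + 2s), so the mean is (4s + i)/5. For IV it is (4i + s)/5. The difference is 0.6(s − i). With s = i it is zero and the artefact cancels. A real difference in visit-dated findings would be diluted by 40%.

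**Step 5: thyroid, taken separately.** From Cycle 1 Day 1 to Cycle 5 Day 1 is 4 × 21 = 84 days, of which 63 (75%) are on the first route and 21 (25%) on the second. The last dose before the Cycle 5 test is the Cycle 4 dose, so either allocation puts a finding dated that day after the switch. The tie plays no part. With an assumed constant hazard and a cumulative risk of 5–10% by then, about 75–76% of cases would have arisen on the first route. The documents give no onset data to support or refute that assumption.

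**The case against.** The strongest reply is that the rule is ambiguous rather than wrong, and that little turns on it. Much of this stands.

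- *The text does not say that the second route is charged.* Both routes have been received on or before Cycle 4 Day 1, and no latest-dose rule is written. The misplacement is the likely implementation, not a stated one. A rule that does not decide still needs a sentence.
- *Other provisions shrink the group.* Events that began in Cycles 1–3 stay with the first route. Under Protocol 5.3.5.2, a diagnosis that replaces recorded symptoms is entered "with a starting date that corresponds to the starting date of the first symptom of the eventual diagnosis". Protocol 4.5 makes dosing depend on acceptable pre-dose results, so a finding that stops the dose creates no tie. Protocol 5.3.5.5 does not make every laboratory abnormality an adverse event. None of this reaches a new, asymptomatic finding dated that day in a participant who is then dosed.
- *Laboratory and vital-sign tables.* A reader might infer that these carry the same bias. The SAP does not support that. SAP 4.3 defines the treatment periods as cross-over and continuation and makes the two halves of the cross-over optional. SAP 4.3.3.2 summarises vital signs by sequence over time.
- *Thyroid.* A reader might infer that every thyroid abnormality found on schedule is charged to the post-switch route, or that thyroid function is first tested at Cycle 5. Neither holds. Tests are scheduled at screening and Cycle 1 Day 1, and a participant who stops during Cycles 1–3 has one at the end of treatment visit.
- *Moving all same-day events to the earlier route could hide acute effects of the switch.* This is a fair warning, because the documents show no onset time for adverse events. The remedy should therefore move only findings from pre-dose assessments.

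**Conclusion.** The point holds in a limited form. SAP 4.3.2 and Protocol 6.5.1 leave an event that starts on a dosing day before the dose either undecided or, on the natural reading, with a route that could not have caused it. In the switching tables by arm and period, visit-dated findings would look up to 50% more frequent after the switch with no true effect.

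That figure assumes equal detection at each visit, full attendance, and laboratory events dated by their sample, a convention the documents do not state. It covers findings dated to the visit only. It does not cover symptoms with an earlier onset, samples dated before the dosing day, or findings that stop the dose. The share of all adverse events involved is unknown, so the whole adverse event table should not be read as inflated by half. The primary endpoint is untouched and the safety analyses are descriptive. By-cycle tables, if produced, would help to show any clustering at Cycle 4.

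The thyroid point is a separate limit of the test interval. For participants who continue treatment, no scheduled test after Cycle 1 Day 1 comes before Cycle 5 Day 1. A finding first seen then is unattributable rather than demonstrably misplaced.

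**What to change.** In SAP 4.3.2:

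- Allocate an event to the most recent dose given before its onset.
- If an event starts on a dosing day and is identified from that day's scheduled pre-dose laboratory, vital-sign or examination assessment, allocate it to the previous dose.
- Leave all other same-day events with that day's dose, including infusion-related, injection-related and cytokine release reactions and anything seen in the post-injection vital signs of Protocol Table 3.
- State which date an asymptomatic laboratory event takes.

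In SAP 4.3.3.1, if the Cycle 1–3 and Cycle 4–6 subperiods are used, put Cycle 4 Day 1 pre-dose values in the first and Cycle 7 Day 1 pre-dose values in the second.

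Footnote the thyroid results: abnormalities first detected at Cycle 5 Day 1 are not attributable to a route. This needs no change to the test schedule.

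The cost is SAP wording and a derivation that matches events dated on a dosing day to that day's assessments. Reactions can be picked out from their recorded diagnosis and dedicated form (Protocol 5.3.5.1). The downside is that a few same-day events without a pre-dose marker may still go to the wrong route.
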